9. RESEARCH METHODS

9.1 STUDY DESIGN

This is an observational cohort study based on existing data.

BOEHRINGER INGELHEIM Group of Companies**NIS Protocol Template****Study number: 1484.0014****Page 12 of 30****Document number: <insert>****9.1.1 Study population**

Study inclusion criteria: All patients ≥ 50 years, with a GA diagnosis in at least one eye, including in the [REDACTED] database identified during the study period (January 2015 to April 2023).

Exclusion criteria: Patients without the information of laterality will be excluded.

No other exclusion criteria are applied for the identification of the study population and description of the patients and eye at baseline.

Additional note:

For certain analysis the patient population will be restricted to those with at least 12, 24, 36, 48, or 60 months of history following diagnosis of GA. For the analysis requiring a VA reading, a restriction to those patients with valid VA readings at the index diagnosis and the respective follow-up times will be applied.

For analysis estimating the size of the GA population relative to other retinal diseases, the same timeframe requirements that the study population will be applied. In this population, any patient in the database will be eligible, and the diagnosis of DME, DR or other conditions may be used for subgroup comparisons.

Primary Disease Definitions

In the [REDACTED] Database, retinal and other diseases are identified using the International Classification of Diseases (ICD), Tenth Revision, Clinical Modification. ICD 10 codes were launched in the USA in October 2015, and are the only version of ICD codes with adequate descriptions of GA and dry AMD severity. As such, only ICD 10 codes will be analyzed in this study and the study period defined above is directly related to the launch of ICD 10 plus a small buffer allowing for physician familiarity.

These codes are entered by the physician at patient visit, with an associated laterality. This, along with the ICD 10 laterality is used in combination to confirm in which eye the disease is occurring. For this study, a patient eye will be considered to have the study disease so long as there is an accompanying ICD code. The primary study diseases to be analyzed are dry AMD, GA and wAMD, and will be identified using the ICD codes in Table 1 below.

Table 1. Study disease definitions-codes.

Study Disease Definitions			
	Dry AMD*	Dry AMD with GA*	wAMD*

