Prevalent visit – all visits following the incident visit in patient eye history while identified with GA in the [REDACTED] database. Prevalent visits may occur year after year throughout the patients' journey.

Study period

Patients will be identified from January, 2015 to April, 2023.

Selection period: Eligible patients must have at least one GA diagnosis between October 2015 and April 2023. The date of the first GA diagnosis will be considered as index date. For all follow up analysis, eligible patient eyes should be divided in those with at least 12, 24, 36, 48 and 60+ months of follow up. follow up requires multiple visits spanning over the outlined durations and total follow up is defined as the time between incident diagnosis and the final visit in the dataset.

BOEHRINGER INGELHEIM Group of Companies**NIS Protocol Template****Page 14 of 30****Study number: 1484.0014****Document number: <insert>**

Follow-up period: up to 60-month period following the index diagnosis date of GA (exploratory follow-up of 1, 2, 3, 4, 5 years may be run as cutoff points)

Pre-selection period: January 2015-September 2015. This period will be used to identify patients who have dry AMD using ICD9 coding, and will help to assign patients into the incidence or prevalence status.

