- Follow up reading at Month 24, 36, 60: +/- 60 days

Incidence (new cases) and prevalence of GA will be captured, based on the ICD 10 diagnosis codes. On a calendar basis, all newly diagnosed patients will be identified and count as incident patients. Patients with a previous diagnosis of GA in the past years (with respect to a given calendar year), will be counted as prevalent cases during that calendar year.

The yearly counts of newly diagnosed or prevalent cases, will help to understand the progression of the overall disease.

BOEHRINGER INGELHEIM Group of Companies**NIS Protocol Template****Study number: 1484.0014****Page 18 of 30****Document number: <insert>****9.3.2.2 Secondary outcomes****• Retinal Disease Related HCRU Outcomes**

Change in physician care over time will be evaluated from the incident date of GA, and assessed on a yearly basis in order to assess if physician habits have changed over time, particularly following September 2021 and additionally following [REDACTED].

Patient visits: A patient visit (or encounter) is identified in the database any time a patient visits one of the panel physicians. Since the [REDACTED] database consists only of private practicing retina specialists, these are the only types of visits analyzed in the study.

If a patient visits the physician at a hospital, institution, or has an emergency room admission, the event will not be captured. For all patient visits, it is assumed that both eyes are being seen/assessed even in the primary visit reason is for one particular eye. In this sense, all visits will contribute to both eyes and any outcomes at these visits will be available for assessment.

Treatments: The documentation includes **all treatments** including injections, laser treatments, and other procedures. The type of diagnostic procedure done, and the results of these diagnostics are also recorded for most encounters. For any visit, it is assumed that both eyes are being seen, even if only one eye receives any treatment.

Other medical procedures: for example, cataracts removal, eye lid (ptosis correction), etc.

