9.3.3 Covariates

9.3.3.1 Demographic Characteristics: The demographic variables below are identified at the patient eye level and will be used to describe the demographic characteristics throughout the analysis. These demographic characteristics will be analyzed at the index diagnosis, unless specified elsewhere.

Age: will be calculated based on DOB from index diagnosis (incident visit).

Sex: identified at index diagnosis, or other visits if not specified.

Diagnosis year: Identified as the calendar year of the index diagnosis.

Months of History: will be defined as the time from index diagnosis to their last record in the database.

Incident Visit: The first visit in the database where one of the study diseases is identified, per eye. This may include Dry AMD, GA and/or wAMD. At incident visits all clinical characteristics, ocular comorbidities, etc. will be also captured.

Prevalent Visit: The first visit during a time period of interest where one of the study diseases is identified, per eye. This may include Dry AMD, GA and/or wAMD. This visit must not be the first diagnosis in the entire patient history. At prevalent visits changes in the clinical

BOEHRINGER INGELHEIM Group of Companies**NIS Protocol Template****Study number: 1484.0014****Page 19 of 30****Document number: <insert>**

characteristics, ocular comorbidities will be captured and described based on the first prevalent visit per calendar year.

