For all time to event metrics, mean (SD), median and range will be summarized, while proportions will be summarized using N (%).

Kaplan Meier or Cox Hazard ratios may be applied when analyzing disease progression. Additionally, it will be determined how patients progress during the 1,2,3,4,5 years follow up according to the lesion location, and lesion size.

Analysis for objective:

To determine the occurrence of GA in the study eye during the study period (at the 12 (24, 36, 48, 60) month follow up period).

The calculation of the occurrence (new cases) of GA will be tracked against the overall number of patients included in the retinal specialist database (████████ database) in a time period (year) as the denominator initially.

The analysis to calculate the prevalent cases will include all patients with a GA diagnosis active in the database in the given time period in the numerator, and all patients included in the retinal specialist database (████████ database) will be used as the denominator initially.

Since, this analysis is referring to a population attending a retinal specialist during a given time period and therefore is not a general population-based estimates, in order to give a context to the data, the proportion of other common diagnosis in patients over 50 years or older attending the clinic in the same time period (e.g. diabetic macular edema, diabetic retinopathy, proliferative diabetic retinopathy, and wAMD) will be calculated. The denominator will be all patients attending to the retina specialist in the given time period using the age group category that is applicable in this study (50 years or older).

For the initial calculations, the look back period in 2015 will be used to discard patients with prevalence GA diagnosis in the subsequent years. prior diagnosis will be excluded and only new cases diagnosis in the time period will be considered in the numerator when calculating incidence.

The calculations will be conducted by calendar year, and absolute numbers (n) and correspondent percentage (%) will be provided. As a sub analysis, it will be evaluated if changes occurred after the third quarter of 2021, corresponding with the ██████████

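### The calendar-year GA tables include a four-month 2023, and possibly a three-month 2015, with no rule for incomplete years; the 2023 new-case count and incidence percentage will read too low

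*Combined protocol and SAP*

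**What the plan says.** Section 9.7.1 (Main analysis) sets the reporting unit for new and prevalent GA: "The calculations will be conducted by calendar year, and absolute numbers (n) and correspondent percentage (%) will be provided". Its later list of outputs stratifies both measures by index year, and section 9.3.3.1 defines that year: "Diagnosis year: Identified as the calendar year of the index diagnosis".

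The time window is in section 9.1.1. Under the selection period: "Eligible patients must have at least one GA diagnosis between October 2015 and April 2023". On coding: "ICD 10 codes were launched in the USA in October 2015", and "only ICD 10 codes will be analyzed in this study". Table 1 gives no ICD-9 code for GA. The look-back is set out as "Pre-selection period: January 2015-September 2015", so October to December 2015 belongs to the selection period.

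Two planned readings depend on the annual series. Section 9.3.2.1 says: "The yearly counts of newly diagnosed or prevalent cases, will help to understand the progression of the overall disease". Section 9.7.1 adds a sub-analysis of whether occurrence changed after the third quarter of 2021.

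Nothing in the plan drops, rescales or flags 2015 or 2023, and the limitations in section 9.9 do not mention incomplete years.

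**The concern.** Followed as written, the plan puts a four-month 2023 in a row with seven complete years. A percentage does not repair this by itself. New cases accumulate in proportion to calendar time. Distinct attendees do not, because many patients seen in January to April are seen again later in the year.

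The stake is a false fall at the end of the series. It would fall in the later period of the comparison around the third quarter of 2021. Only one complete calendar year (2022) follows that date, so the short 2023 point could be taken for a real change. At the other end, a 2015 point would rest on three months in which GA could be coded at all.

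**Working it through.** The plan states no annual rate, so there is no figure to reproduce. The check asks what an unchanged disease would look like in the planned tables.

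**Inputs from the documents.** GA countable from October 2015 to April 2023 (9.1.1); calendar-year n and % (9.7.1); 72,718 GA patients in the feasibility count from 2016 (9.5).

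**Assumptions.** New cases accrue evenly. The feasibility count spans January 2016 to April 2023 (88 months); its end date is not stated. Visits follow a Poisson process with v per year, so P(seen within t years) = 1 - exp(-vt). The denominator is patients attending in the same months. The documents give no visit rates, so v is varied.

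**1. Coverage.** 2015: 92/365 = 25.2% of the year. 2023: 120/365 = 32.9%. The years 2016-2022 are complete.

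**2. New-case count, 2023.** 72,718/88 = 826.3 per month. Full year: 12 × 826.3 = 9,916. January-April: 4 × 826.3 = 3,305, or -67%. The absolute numbers only illustrate scale; the ratio of one third needs only even accrual.

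**3. Incidence percentage, 2023.** Ratio to the full-year value = (1/3) / [(1 - exp(-v/3)) / (1 - exp(-v))].

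| Visits per year (v) | Attendees in 4 months / attendees in 12 | Incidence % / full-year value |
|---|---|---|
| 1 | 0.448 | 0.74 |
| 2 | 0.563 | 0.59 |
| 4 | 0.750 | 0.44 |
| 6 | 0.867 | 0.38 |
| 12 | 0.982 | 0.34 |

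The direction does not depend on v. Split a year into three similar four-month blocks: new cases add up across blocks, but distinct attendees overlap, so each block holds more than a third of the year's attendees.

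**4. Prevalence percentage, 2023.** Both numerator and denominator are distinct patients seen. With GA patients at g visits per year and all attendees at v, the ratio is [(1 - exp(-g/3))/(1 - exp(-g))] / [(1 - exp(-v/3))/(1 - exp(-v))].

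- g = 2, v = 2: 1.00
- g = 2, v = 4: 0.563/0.750 = 0.75
- g = 2, v = 6: 0.563/0.867 = 0.65
- g = 4, v = 2: 0.750/0.563 = 1.33

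The shift can be nil, downward or upward.

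**5. A 2015 point, if shown.** With three months of GA coding over a 12-month denominator, prevalence would read (1 - exp(-g/4))/(1 - exp(-g)) of its full-year value: 0.40 at g = 1.5, 0.46 at g = 2, 0.64 at g = 4. New cases have no clear direction. A patient with existing GA seen in October-December 2015 receives a first GA code then and counts as new. Suppose 5 of 100 yearly attendees have GA and 2 are truly new in a year. Then 5 × 3/6 = 2.5 would be coded new if patients attend every 6 months, and 5 × 3/12 = 1.25 if every 12 months. These lie on either side of the true 2.

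**6. 2016.** The year is complete in time, but section 9.7.1 relies on 2015 for clearing out earlier cases: "the look back period in 2015 will be used to discard patients with prevalence GA diagnosis in the subsequent years". At most three months of that year can carry a GA code, so existing GA first coded in 2016 still enters as new.

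**The case against.** The outputs are descriptive, the April 2023 cut-off is openly stated, and section 9.7.1 already warns that these are not general-population estimates. A careful reader would discount a four-month year. A 2015 point may not be intended either: section 9.7.1 treats 2015 as look-back, section 9.1.1 speaks of a short allowance after the ICD-10 launch, and the feasibility count starts in 2016.

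Part of this stands. Whether 2015 will be tabulated is open, and no passage says that a 2015 denominator would run for 12 months. But none of these passages limits the annual tables, and they leave 2023 untouched. A stated cut-off date also does not tell the reader that the 2023 percentage is biased as well as the count.

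A reader might infer more than the documents support:

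- **GA prevalence, and GA relative to diabetic retinopathy, diabetic macular edema or wAMD, must drop in 2023.** This requires GA patients to attend at a different rate from the comparison group, and no rates are given. GA and wAMD can coexist in one patient or one eye (9.1.1), so some GA patients may attend as often as treated wAMD patients.
- **New cases will look low in 2015.** Step 5 shows that they could be too high.
- **Every trend in the study is affected.** Visual acuity change, progression and Kaplan-Meier analyses run from the index or diagnosis date, not by calendar year.

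**Conclusion.** The concern holds for 2023. The new-case count will be about one third of a full year (about -67%) if accrual is even. The incidence percentage will be too low, at about 0.34 to 0.74 of its full-year value for an assumed 12 to 1 visits per year; the direction is firm and the size rests on that assumption. The comparison around the third quarter of 2021 is exposed because the short point lies in its later period.

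Prevalence percentages and between-disease comparisons for 2023 are at risk only under unequal attendance. A 2015 point, if produced, is not interpretable: prevalence would be low if a 12-month denominator is used, and new cases could err either way. Starting in 2016 solves the problem of incomplete time but does not make 2016 new cases comparable with later years. Analyses by time since index are not touched.

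**What to change.** Add to section 9.7.1:

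- Annual n and % are given for complete calendar years only, 2016-2022, with no annual figure for 2015.
- 2023 is shown only as January-April, beside January-April of earlier years, with numerator, denominator and comparator diseases all limited to those months.
- The same rule (complete years or matched months) applies to the comparison around the third quarter of 2021.
- New cases in 2016, including its January-April figure, are flagged as likely to include existing GA, since at most three months of GA coding precede that year.

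Multiplying the 2023 count by 12/4 is not a substitute. Under even accrual it restores the count, but not the percentages, because distinct patients do not grow in proportion to time.

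The cost is a few lines of text and a date filter. The downside is two fewer points in the annual table.

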Data analysis:	
In this study, both patients and eyes will be considered as the analysis unit. Baseline characteristics will be summarized using descriptive statistics. For continuous variables, the mean, standard deviation, median and range will be presented. For categorical variables frequency and proportion will be used. Variables are identified and calculated at the index diagnosis and throughout the follow-up period for primary outcomes like VA.
 
In the progression analysis, the population will be restricted to patients with a minimum follow-up time (i.e. multiple visits at least one year apart, at least two years), or patients with valid VA reading at the index diagnosis and a second follow-up timepoint. [REDACTED]
 
The analysis of incident and prevalent calculations will use as the denominator, all patients referred to the retinal specialist. The proportion of patients with a GA diagnosis referred to the retinal specialist will be put into perspective by comparing to other conditions, such as proportion of patients referred to the retinal specialist with a diabetic macular edema (DME) diagnosis, or with a diabetic retinopathy (DR) diagnosis etc. Additionally, extrapolations will be done to approximate to a population-based estimate.
									
Milestones:	
 
 Start of data collection	05/2023		
 
 End of data collection	06/2023		
 
 Final report of study results	06/2023		
 
	Start of data collection	05/2023		End of data collection	06/2023		Final report of study results	06/2023	
Start of data collection	05/2023									
End of data collection	06/2023									
Final report of study results	06/2023									

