8. RESEARCH QUESTION AND OBJECTIVES

Research Question

To quantify and describe patients with a GA diagnosis in at least one eye. [REDACTED]

Primary objectives

To describe the characteristics* of patients with GA in at least one eye.

To describe characteristics* of the study eye and the fellow eye, at index diagnosis

To evaluate and characterize the progression of newly diagnosed patients with GA during each year for 5-year follow-up period. In particular, to describe patients' characteristics, study eye and the fellow eye characteristics over the 5-years follow up. [REDACTED]

Secondary objectives

To determine the first time occurrence of GA in the study eye, during the study period.

To determine the proportion of patients with GA in the study eye, over the study period.

To compare the GA first time occurrence and the proportion of GA, relative to other retinal conditions, and relative to proportion of retinal specialist contributing to [REDACTED] and the overall US retinal specialist.

To evaluate patients' management (i.e. patients visits and procedures) over the study period.

To describe [REDACTED]

the overall GA population.

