9.2 SETTING**9.2.1 Study sites**

All data in this study is de-identified, from existing electronical health records from the retinal specialist practices included in the [REDACTED] Database (US).

The [REDACTED] database consists of data from a geographically diverse panel of United States based private retina specialists (RS). [REDACTED] has physician coverage from 2015 onwards, totaling up to 360+ physicians coming from 70+ practices. These practices span across the USA geographically, with the regional distribution as follows: Midwest (20%), Northeast (17%), Southeast (27%), Southwest (11%), West (26%). This collection of practices has contributed 2+ million patients and 13+ million patient visits over the lifetime of [REDACTED] and is estimated to account for 15-20% of all retina specialists practicing in the USA. This dataset represents a collection of private practicing retina specialists in the USA, no data is collected from hospital or public institutions.

The [REDACTED] Database therefore includes longitudinal measures of physician findings and patient outcomes. This includes health related outcomes such as deterioration of visual acuity, poor adherence, subretinal fluid, intraocular pressure, and geographic atrophy. Patient phenotypes and individual outcomes can be described by individual comorbidities, demographics, visits, prescriptions, and other relevant clinical characteristics gathered from clinical codes, patient provided information and text mining of patient notes.

Study Subgroups

Following analysis on the overall population, subjects will be placed into subgroups for further analysis. Below are the proposed subgroups which may be subject to modification following data readouts. An initial feasibility will be run to assess each threshold for each subgroup, following which a final subgroup will be chosen. Any analysis (i.e. description of patients characteristics and progression) on subgroups will be defined below.

- Duration of follow up: 1+, 2+ 3+, 4+,5+ years of history
- Newly diagnosed patients with GA vs. patients with an existing GA diagnosis
- Conversion rates over time – Stratify the population into those that either progress/don't progress in the 1+, 2+ 3+, 4+,5+ years of follow up;
- [REDACTED] in the 1, 2, 3, 4 and 5 years of follow up period.
- Patients [REDACTED] that do not in the 1, 2, 3, 4 and 5 years of follow up period.

- GA lesion location (sub foveal vs extrafoveal)
- GA lesion size.

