An additional analysis will be made to extrapolate the prevalent results to a national – US-level. For that analysis, the prevalence of GA will be considering all patients seen by a retina specialist in the given year. With this metric, estimation on a national level will be done using an estimation of all practicing US retina specialists.

When analyzing the rate of progression from dry AMD to GA, a conversion analysis will be done. This will include the overall rate of dry AMD eyes developing GA, along with a Kaplan Meier analysis assessing the rate of conversion over time. This analysis will track progression by month from diagnosis, censor any patient at the final visit in the database, and identify the incident GA diagnosis as an event.

Analysis for objectives:

To evaluate patients' management (i.e. patients visits and procedures) over the study period.

BOEHRINGER INGELHEIM Group of Companies**NIS Protocol Template****Page 24 of 30****Study number: 1484.0014****Document number: <insert>****Patients' management**

All visits, treatment, checkups, procedures, and other will be summarized across the duration of the study time frame as well as between the index diagnosis and at the 12 (24, 36, 48, 60) month follow up period.

An additional sub analysis will be conducted to evaluate the changes in the frequency of patients visits or procedures, checkups, after the third quarter of 2021 and after [REDACTED].

Summary will include descriptive statistics; continuous variables will be described by absolute numbers, the mean (SD), median and range, while categorical variables will be described using frequency and proportion. Absolute numbers (n), and correspondent percentage (%) of the variables (either eyes or patients as appropriate) will be always included in the description of the results.

Analysis for objective:

To describe and compare patients' characteristics in different progression subgroups (i.e. those that develop eCNV/those that not), of the overall GA population.

The following groups will be evaluated to better understand progression:

1. Patients that [REDACTED]

vs. those that do not in the 1, 2, 3, 4 and 5 years of follow up period.

2. Patients that [REDACTED]

vs. those that do not in the 1, 2, 3, 4 and 5 years of follow up period.

3. Patients with subfoveal lesion location vs. those with extrafoveal lesion location.

For this subgroup of patient's characteristics will be described and compared.

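### The national GA estimate is planned without a range, although the plan's own panel coverage of 15-20% alone moves it 1.33-fold, and it describes retina-specialist patients rather than the population.

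*Combined protocol and SAP*

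**What the plan says.** Section 9.7.1 (Main analysis) states: "An additional analysis will be made to extrapolate the prevalent results to a national – US-level". The prevalence used is that among patients seen by a retina specialist in the given year, and "estimation on a national level will be done using an estimation of all practicing US retina specialists". No formula, source for the specialist number, or low and high scenario follows. For the incidence and prevalence calculations the section plans counts and percentages by calendar year. Section 9.6 mentions confidence intervals only in a general list of what the software will do.

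The extrapolation relates to a secondary objective in section 8, which sets GA against the share of contributing specialists and "the overall US retinal specialist".

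Section 9.2.1 describes the panel. It has been covered since 2015, "totaling up to 360+ physicians coming from 70+ practices", and "is estimated to account for 15-20% of all retina specialists practicing in the USA". It consists of private practices, and "no data is collected from hospital or public institutions".

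On interpretation, section 9.7.1 says that the clinic analysis refers to people attending a retina specialist and "therefore is not a general population-based estimates". The abstract (section 4, Data analysis) says that "extrapolations will be done to approximate to a population-based estimate". The limitations in section 9.9 do not discuss the national extrapolation.

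**The concern.** A national count is easily quoted without its context. Here the scaling factor is itself an estimate, and the plan already knows it only as a range. If one specialist number is used and one figure reported, readers cannot see that the plan's own inputs allow materially different answers.

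Two further assumptions go into the figure unstated. First, scaling from a private-practice panel to all practicing specialists gives hospital and public specialists the panel's GA caseload, which the database cannot observe. Second, a count built from specialist attendance covers only people who reach a retina specialist. Multiplying by the number of specialists changes the scale of the count but not whom it describes. Under the abstract's wording, a reader could take the result as the number of people in the US with GA.

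**Working it through.** The documents give no national estimate, US specialist total or interval, so there is no figure to reproduce. The check asks how far the plan's own coverage range moves the result.

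**Inputs from the documents**
- Panel share of US retina specialists, s: 15% to 20% (section 9.2.1).
- Panel size: about 360 physicians (section 9.2.1, which says up to 360+).
- GA patients at feasibility: 72,718 (section 9.5). This is cumulative from 2016 and uses ICD-10 codes plus exam notes. The planned extrapolation is for a given year, so the count serves only as an illustration.

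**Formula (the natural reading of sections 8, 9.2.1 and 9.7.1 together)**

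National count = panel count / s.

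**Step 1. Spread from the share alone, independent of the count**
- High end over low end: 0.20 / 0.15 = 1.33.
- Relative to the midpoint s = 17.5%: 0.175 / 0.20 - 1 = -12.5%, and 0.175 / 0.15 - 1 = +16.7%.

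**Step 2. Illustration with the cumulative count**
- s = 20%: 72,718 / 0.20 = 363,590.
- s = 17.5%: 72,718 / 0.175 = 415,531.
- s = 15%: 72,718 / 0.15 = 484,787.

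These are not forecasts of the study's annual US estimate.

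**Step 3. The same range as a number of specialists**

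Taking the panel as exactly 360: 360 / 0.20 = 1,800 and 360 / 0.15 = 2,400. Reporting at both ends of the specialist number is therefore the same as reporting at 20% and 15% coverage for the current panel.

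**Step 4. What the share range leaves out**

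Let r be the GA caseload of a non-panel specialist relative to a panel specialist. Then

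National count = panel count × [1 + r(1 - s)/s].

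Setting r = 1 gives back the simple division. The documents give no value for r, so 0.75 and 1.25 are assumptions.

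| r | Multiplier, s = 20% | Multiplier, s = 15% |
|---|---|---|
| 0.75 (assumed) | 4.00 | 5.25 |
| 1.00 (implied by the plan) | 5.00 | 6.67 |
| 1.25 (assumed) | 6.00 | 8.08 |

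With the illustrative count, the range widens from 363,590 to 484,787 (r = 1) to 290,872 to 587,804 (r from 0.75 to 1.25). A 15-20% range is thus a minimum statement of uncertainty.

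**The case against.** The strongest reply is that section 9.7.1 does not write out the arithmetic. It does not commit to a single value or to fixed coverage, and its yearly framing is compatible with year-specific scaling. That stands: the text shows that the formula and range are unspecified, not that a falsely precise number was chosen. But no range is planned for a factor the plan already knows as a range, and nothing else in the documents supplies one.

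It may also be said that the private-practice setting is openly disclosed, that section 9.7.1 defines its quantity by retina-specialist attendance, and that section 9.9 regards severe AMD as handled only by retina specialists. The first two are true, but neither caveat is carried to the national figure. The third does not help with unobserved hospital and public specialists, and section 9.9 itself allows that a patient may have been diagnosed earlier by an ophthalmologist.

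Four stronger readings are tempting, and the documents do not support them:
- *The US trend would rise artificially because the panel grew.* This needs both a growing panel and a fixed share. No yearly physician counts are given and no fixed share is stated, so neither the rise nor any size for it can be asserted.
- *The plan would put a misleading binomial interval on the national figure.* No such interval is proposed.
- *The abstract contradicts section 9.7.1.* The caveat concerns raw clinic proportions, and the abstract offers extrapolation as a response to it. The two are in tension, not contradiction.
- *Patients are counted twice.* Section 9.4 says that records are continuous only within a practice, but adjoining text is redacted and may cover linkage. Duplication is possible, not shown.

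**Conclusion.** The point holds in a limited form. The national estimate has no planned range, although the plan's own coverage figure produces a 1.33-fold spread, or -12.5% to +16.7% around 17.5%. That size rests on scaling by physician share and on the stated 15-20%, and it does not depend on the patient count. The result also assumes equal GA caseload among specialists outside the private panel, which these data cannot test. What it estimates is GA patients under retina-specialist care, not a population-based quantity. The analysis is additional and relates to a secondary objective, so no primary objective is affected. The change should still be made, because it alters the figure reported and what can be concluded from it.

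**What to change.** In section 9.7.1:
1. State the formula and the source of the US specialist number.
2. For each calendar year, scale by the panel physicians active in that year: national count = GA patients in the year × US specialists / panel physicians active in the year.
3. Report the national figure at both the low and high ends of the specialist-number estimate, equivalent to 20% and 15% coverage for the current panel.
4. State that this range does not cover caseload differences between panel and other specialists, or possible duplicate patients across practices.
5. Label the result *GA patients under retina-specialist care, assuming private-practice caseload*.

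In the abstract, replace the population-based wording with the same label.

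The cost is a count of active panel physicians by year, a few lines of calculation and some rewording. No new patient data are needed. The downside is that a single headline number becomes a wider range.
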